1.0 BACKGROUND AND HYPOTHESES

There are an estimated 1.2 million people who inject drugs (PWID) in the US.^{29,30} Injection drug use dramatically increases risk for blood borne infectious diseases, endocarditis, soft tissue infections, drug overdose, psychiatric disorders, and mortality.³¹⁻³⁸ Despite this, there are few interventions to prevent drug injection initiation, and we are not aware of any that have been proven to be efficacious in a rigorous, large randomized controlled trial (RCT).³⁹⁻⁴³

To address this critical public health need, we propose to conduct a large-scale RCT of "Change the Cycle" (CTC)^{.7,44} an hour long, single-session, one-on-one intervention that aims to reduce injection initiation by encouraging active PWID to not promote drug injection, model injection behavior, describe how to inject, or assist in injection initiations of non-injectors. This approach is informed by social learning theory, which postulates that people learn behaviors through interaction, observation, behavioral experimentation, and reinforcement.^{1,2} These constructs are all highly relevant to the prevention of injection initiation; existing research convincingly demonstrates that *interactions* with active PWID who describe injection, observations of injection drug use, and *reinforcing* conversations that promote the advantages of drug injection (e.g., the better "high" to be gained from injecting) contribute to injection initiation.⁴⁵⁻⁵⁶ Further, retrospective accounts of injection by an active PWID.^{48,57} Therefore, intervening on active PWID to reduce describing how to inject to non-injectors (*interaction*), injecting in front of non-injectors (observation), speaking positively about injection drug use (*reinforcement*), and assisting in first injection (*experimentation*) could be a promising approach for reducing uptake of injection drug use.

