2.0 OBJECTIVES AND PURPOSE

To achieve these aims, people who inject drugs (PWID) who report having initiated someone or having injection initiation social learning risks in the past 6 months (N=1,076) will be randomly assigned to receive CTC or an equal attention control condition in Los Angeles (LA) and San Francisco (SF), CA. Injection initiation

and injection initiation social learning variables will be collected at baseline, 6 months, and 12 months. CTC is brief, easy to implement, and novel in its focus on active PWID as a conduit for preventing injection initiation. If proven efficacious, CTC will be a much-needed, practical approach to preventing drug injection initiation.³⁹⁻⁴³

The main outcomes by Aim are as follows: 1) Counts of non-injectors initiated into drug injection at 6 and 12 months; 2) Counts of request to initiate a non-injector into drug injection at 6 and 12 months; and 3) Counts of noninjectors initiated into drug injection and request to initiate non-injectors at 6 and 12 months. The study will be implemented in 2 phases. Phase 1 involves adaptation and training of intervention personnel and Phase 2 involves implementing the full study.

Elucidation goals are to better understand issues related to 1) HAV/HCV effects and 2) drug effects and withdrawal and symptoms management PWID.

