3.9. Baseline interviewing. Baseline interviews will be conducted in English using computer assisted personal interview. The interview will occur in an one-on-one session with a trained research interviewer. Participants will receive \$15 for completing the screening interview. We will conduct approximately 48 baseline interviews per month (24 interviews at each site per month) until 538 participants have completed the CTC intervention and 538 participants have completed the equal attention control intervention (*Timeline, Table 1* see below).

The elucidation study interviews will be offered to current study participants. Study 1 (HAV/HCV) is a quantitative survey that covers topics related to HAV risk (sanitation issues) and HCV treatment (Appendix N). Study 2 is qualitative in nature and addresses effects and withdrawal symptoms (Appendix O). Procedures in section 3.10 to 4.0 do not apply to the elucidation study.

3.10. Randomization. Following completion of the interview each participant will be randomly assigned (using urn,⁸⁹ see **Section 6.0**) to receive either the CTC intervention or the equal attention control nutrition intervention session, according to a computer-generated random numbers program. 3.11. Intervention fidelity and quality control. All intervention trainings will be audio-recorded. To ensure intervention fidelity, the Study Coordinator will listen to all recorded trainings for the first month and then a 10% random sample thereafter. The Study Coordinator will score intervention fidelity on a standardized form that will include a list of all intervention manual components. Interventionists will receive reports from these sessions. If interventionists score less than 95% fidelity on any session, they will be retrained by the Study Coordinator and tape recordings of their next sessions will be reviewed until a 95% fidelity rate is obtained. Given our past experience, training plan and oversight, we expect fidelity to rarely fall below 95%. Participants will also complete a short questionnaire on their satisfaction with the intervention session to which they were exposed (see **Appendix K**).

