3.15. Data collection measures. Data collection measures were selected based on their relevance to evaluating CTC, applicability to social learning theory and IMB model, and potential as confounders. Items from each area are described below and a draft of the baseline questionnaire is included in **Appendix H**.

3.16. Main outcome measures for **Aims 1 & 3** will be the number of people initiated in the past 6 months. This item will be assessed by asking the following questions: "In the past 6 months, have you helped someone get their first hit (the first time they ever injected)?" If participants respond Yes, they will be asked the following question: "How many people (total) have you helped get their first hit (inject for the first time) in the past 6 months?" Not applicable responses (or No on the first item) will be recoded as zeros for data analysis purposes. For **Aims 2 & 3** we will ask the following items: "In the past 6 months, have you been asked to help someone inject an illicit drug for the first time?" Participants responding 'yes', were then asked how many people had asked them to provide their first injection. The time frame of 6 months allows us to assess changes in the outcome at 6 months (as was done in the pilot) and 12 months. The use of a count approach for outcome variables enables us to account for changes even if they only occur among high volume initiators and those with multiple injection initiation social learning risk. We will also collect data on sex risk, specifically, unprotected sex, multiple sex partners, and sex risk by partner type^{91,92} for purposes of determining the efficacy of the attention control condition although this is not an aim of the proposed study.

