Aim 1: To test the efficacy of CTC on reducing the number of non-injectors initiated into injection (counts) by PWID. Hypothesis 1(H1): PWID who receive CTC will report initiating fewer non-injectors into drug injection at 6 and 12 months as compared with PWID in the equal attention control condition. To test H1, we will conduct structural equation modeling (SEM) using Mplus (release 7.11).99 Our primary outcome analysis is based on an outcome that is distributed as counts of the number of episodes initiating someone into drug injection. This is a standard Poisson count variable with a potential inflation of the number of zeros as there will likely be many who do not initiate others (e.g., zero-inflation). This Poisson count outcome can essentially be thought of as consisting of two separate, yet interrelated, processes-one in which the participant engaged in the behavior of initiating someone else at all (i.e., binary yes/no) and another in which we assess the number of times the participant initiated someone (ranging from 1 to j, where j=the number of episodes initiating someone. In SEM literature, this is referred to as a two-part process for zero inflated Poisson, as SEM models these two processes separately as unique latent processes.¹⁰⁰ As this outcome is collected as part of an intervention with a baseline (T0) and two follow-ups (T1, T2), the model is parameterized to accommodate three time points, following Olsen and Schafer (2001).¹⁰⁰ Note that with three time points, the implied model is mis-identified given the number of measured variables in the variance-covariance from the observed data in an SEM measurement model with an intercept (i) and slope (s) for 3 observations.¹⁰¹⁻¹⁰³ However, joint modeling the ZIP as a two-part process redresses the identification problem, and results in 6 measured variables, one for the process in which the participant actually initiated another person (0 for no, 1 for yes) and another for the

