Aim 3: To test whether injection initiation social learning risks (injecting in front of, describing injection to, and speaking positively about injection to non-injectors) act as mediational mechanisms for the efficacy of the CTC intervention on initiation and request-to-initiate outcomes. H3: Social learning variables will significantly mediate the association between the CTC intervention and episodes of initiating and being requested to initiate someone into drug injection at 6 and 12 months. The outcome variable will remain counts of the number of episodes initiating someone into drug injection (Aim 1) and the counts of request to initiate another person (Aim 2). The mediational models will be specified following the work of Baron and Kenny and newer generalizations.¹⁰⁶⁻¹⁰⁸ With only three time points, we can examine the effect of baseline randomization to treatment status on 12-month counts of injection initiation as the outcome and 6-month injection-risk behavior variables as the mediators. The lagged approach can be used as static measures at 6 months and 12 months, or changes in injection initiation social learning risks and IMB skills constructs that precede changes in the number of counts of initiation as outcome. This latter approach is strong in that the change in a variable, created by difference scores, is isolated so that it precedes the subsequent outcome.

There are also techniques for estimating mediational models with only 2 time-points;¹⁰⁹ consequently, we will examine mediation from randomization to 6-month follow-up with the mediator and outcome measured concurrently. We can estimate separate mediational models for each injection initiation social learning risk and IMB skills construct, or enter the mediation mechanisms together into a single model, while examining overfit due to multiple mediational paths.¹¹⁰ Omnibus measures of model fit (chi-square, root mean square error of approximation, Tucker Lewis Index [TLI]), and specific path coefficients will be used to assess the treatment effect and test for the mediational pathways. The null hypothesis will be rejected if the p value for the variable that denotes treatment condition is below 0.05. Proposed Co-I [name] has extensive experience with these techniques as part of longitudinal community-based interventions.^{105,111,112}

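### The change-on-change mediation option that Section 13.1 calls strong most naturally subtracts a post-session 6-month count, so a sustained effect mediated within the same window cancels out of it

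*Combined protocol and SAP*

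**What the plan says.** The Aim 3 text of Section 13.1 sets out a lagged mediation analysis in two permitted forms. One is static: the 6-month mediator and the 12-month count. The other uses "changes in injection initiation social learning risks and IMB skills constructs that precede changes in the number of counts of initiation as outcome". Of the second it says: "This latter approach is strong in that the change in a variable, created by difference scores, is isolated so that it precedes the subsequent outcome". It does not state which interval the count change covers. It also commits to a concurrent model with mediator and outcome both taken at 6 months. No mediation model is named as primary.

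Four features of the design bear on this:

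- CTC is "an hour long, single-session, one-on-one intervention" (Section 1.0).
- Assignment comes straight after the baseline interview: "Following completion of the interview each participant will be randomly assigned" (Section 3.10).
- Injection initiation "and injection initiation social learning variables will be collected at baseline, 6 months, and 12 months" (Section 2.0).
- The outcome question looks back six months: "How many people (total) have you helped get their first hit (inject for the first time) in the past 6 months" (Section 3.16). The mediator items in Section 3.17 are yes/no questions with the same recall period.

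H1 and H3 refer to effects at both 6 and 12 months.

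**The concern.** Three visits give two consecutive intervals. For one change to come before another, the mediator change has to be months 0 to 6 and the count change months 6 to 12. The 6-month count then serves as the starting value of the outcome. That count covers roughly the first six months after the session, so it already carries whatever CTC has done by then. Subtracting it removes that part of the effect.

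The temporal ordering that makes this option attractive is therefore bought by discarding the early effect. An analyst who follows the plan's endorsement could report no mediation, or mediation of the wrong sign, when CTC has worked early and durably through the social learning risks.

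**Working it through.** **Inputs from Section 13.2.** 809 PWID initiated 431 people in a year; the intervention is expected to halve initiations; 1,076 are randomised 1:1; attrition is 25%; the pilot showed a 38% reduction in injecting in front of injection-naive people.

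**The plan's own figures reproduce.** 431/809 × 1,076 = 573; 431/809 × 538 = 286.6 per arm (stated 286); half of that is 143. Retention: 1,076 × 0.75 = 807 (stated about 800). The plan gives no figure for the change-on-change model.

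**Step 1: arm contrast in the 6-to-12-month change.** The control rate is 431/809 = 0.533 per person-year, or 0.266 per six months if spread evenly (my assumption). Halving gives a difference of −0.133. Y6 and Y12 are the counts at 6 and 12 months. Baseline counts are equal in expectation by randomisation, so the contrast in change from baseline (Y12 − Y0) equals the contrast in Y12.

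| Effect pattern | Y6 | Y12 and Y12 − Y0 | Y12 − Y6 |
|---|---|---|---|
| Halving, sustained | −0.133 | −0.133 | 0.000 |
| Halving, half waned | −0.133 | −0.067 | +0.067 |
| Halving, fully waned | −0.133 | 0.000 | +0.133 |
| Growing from 25% to 50% | −0.067 | −0.133 | −0.067 |
| Halving only after month 6 | 0.000 | −0.133 | −0.133 |

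The zero in the first row does not depend on the base rate.

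**Step 2: the indirect effect.** Let the count depend on the mediator in the same window (coefficient c) and in the previous window (coefficient l): Y_t = constant + c·M_t + l·M_(t−1). Then

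Y12 − Y6 = c·(M12 − M6) + l·(M6 − M0).

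Let a be the CTC effect on the mediator, and let k be the fraction of a 0-to-6-month mediator change that is undone by month 12. The model estimates a·(l − k·c). With a sustained mediator effect the true 12-month value is a·(l + c). If the change fully persists, k = 0. If the three measurements are equally correlated, with no carry-over of the change itself, k = 0.5.

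- Same-window only (l = 0): the estimate is −k·a·c. It is zero at k = 0, and half the true size with the wrong sign at k = 0.5.
- Equal parts (l = c): the estimate is a·c·(1 − k) against a true 2·a·c. Between 50% (k = 0) and 25% (k = 0.5) is recovered, with the right sign.
- Lagged only (c = 0): the estimate is a·l, which is fully recovered.

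**Step 3: simulation with a sustained effect and complete same-window mediation.** Two sets of assumptions were used. Apart from the 38%, the mediator and count settings are not in the documents.

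*Set A:* 400 per arm, 1,000 runs; 60% endorse the mediator at baseline; CTC switches off 38% of it; mean counts are 0.42 with and 0.10 without the mediator; joint significance test. The true indirect effect is 0.60 × 0.38 × 0.32 = 0.073, as a reduction.

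| Mediator persistence | 0.5 | 0.7 | 0.9 | 1.0 |
|---|---|---|---|---|
| Change-on-change, mean indirect effect | +0.012 | +0.006 | +0.002 | 0.000 |
| Change-on-change, significant in wrong direction | 22% | 8% | 4% | 2% |
| Static lagged, mean indirect effect | −0.044 | −0.056 | −0.067 | −0.073 |

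Change-on-change was significant in the right direction in 0% to 2% of trials. The static model, adjusted for baseline mediator and count, was so in 98% to 100%.

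*Set B:* N = 800, 1,500 runs; baseline mediator prevalence 0.5 or 0.7; rate ratio for the mediator 3 or 6; trait stability 0.3 to 0.8; Sobel test.

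| Model | Right direction, significant |
|---|---|
| Change-on-change, Y12 − Y6 | 0% (wrong direction in 41% to 67%) |
| Mediator change 0 to 6, Y12 − Y0 | 95% to 99% |
| Static M6 to Y12, adjusted for M0 and Y0 | 71% to 97% |
| Concurrent M6 to Y6 | over 99% |

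The treatment coefficient on Y12 − Y6, the quantity in the plan's stated decision rule, was significant in about 5% to 6% of runs, which is chance level.

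**Step 4: lagged mediation.** With purely lagged mediation, the Y12 − Y6 model was right and significant in at least 99% of runs. With mediation half lagged, the right sign was found in 67% to 83%.

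**The case against.** The interval is inferred. Section 13.1 does not say that the count change runs from 6 to 12 months. Its second sentence speaks only of a subsequent outcome, and elsewhere the outcome is said to remain the counts. Mediator change 0 to 6 paired with the 12-month count, or with change from baseline, is not ruled out. This stands as a limit on certainty. Even so, the text asks for mediator changes that precede count changes, and a 0-to-12-month count change overlaps the mediator interval, so the wording needs settling in any case.

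A reader might infer that H3 would be rejected, or Aim 3 lost. The documents do not support that. This model is one permitted option; the static lagged form stands beside it, and the concurrent 6-month model is the one the plan commits to. Neither shares the cancellation.

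A reader might also infer that the model fails whenever CTC works and is fully mediated. That needs a mainly same-window effect. Section 7.1 says that lower social learning risk should lead to fewer requests and initiations, without saying how quickly, so lagged mediation remains possible and this model would recover it.

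Finally, the wrong-sign rates depend on assumption. At persistence 0.9 and 1.0 they are 4% and 2%, against 2.5% expected by chance in one tail. The larger rates need low persistence, for which the documents give no figure. A null result is the firmer prediction.

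**Conclusion.** The point holds for this one option. On the natural reading of the intervals, an effect present by month 6 and sustained to month 12, as H1 and H3 allow, gives an arm contrast of about zero in the 6-to-12-month change. Mediation acting mainly within the same six-month window is then missed. That follows from the schedule and the recall period.

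The simulated detection rates rest on complete same-window mediation and the settings listed. A reversed sign is possible, not established. Partly lagged mediation is attenuated, and may reverse if l is smaller than k·c. This is more than missing detail, because the affected version is the one the plan recommends. It is a wording change worth making before analysis; it is not a threat to Aim 3 as a whole.

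**What to change.** In the Aim 3 text of Section 13.1:

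1. Remove the statement that the change-on-change version is strong.
2. Name one main lagged model for H3: arm to 6-month mediator to 12-month count, with the baseline mediator and baseline count as covariates. Note that it can understate a same-window effect when the mediator is not persistent: in set A at persistence 0.5 it returned 0.044 of 0.073, about 60%.
3. Keep the planned concurrent 6-month model.
4. If a change version is kept, write out its intervals and take the count change from baseline (0 to 12 months). Limit any 6-to-12-month count change to an exploratory analysis of effects arising after month 6.
5. Report each indirect effect beside the total arm effect at the same visit. In two set B settings where the effect had fully waned by month 12, the static model still gave a significant protective indirect effect in 64% and 68% of runs, and the change-from-baseline model in 95% and 76%.

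The cost is SAP wording. No new data, visits or participants are needed.

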3.17. Main independent measures will be intervention condition: CTC or equal attention control group for Aims 1 & 2. For Aim 3, we will also evaluate three injection initiation social learning risks as mediating variables. These items are intended to capture social learning constructs (i.e., observation of behavior, supportive interactions, and reinforcement) within the social processes of injection initiation. To capture observing, we will ask current PWID the following item: "In the past 6 months, have you injected drugs in front of someone who has never injected an illicit drug?" To capture interaction, we will ask "In the past 6 months have you explained or described how to inject to someone who has never injected an illicit drug (i.e., a noninjector)?" To measure reinforcement we will ask, "In the past 6 months, have you spoken positively about injecting with someone who has never injected an illicit drug?" Each item is a binary variable (Yes/No) where Yes denotes endorsing the injection initiation social learning risk assessed.

We will also collect IMB constructs related to injection initiation and sex risk. For the information construct, we will collect true or false knowledge items on sex-related HIV prevention provided by Kalichman, Simbayi and others^{5,6} and develop similar items for injection initiation risks. To develop injection initiation risk motivation and behavioral skill items we will follow procedures outlined by Kalichman, Simbayi and others.^{5,6} For sex-risk related motivation and behavioral skill items we will draw from existing studies.^{5,6} All injection initiation risk and sex-related IMB skill items will all be pilot tested. Psychometric properties of existing measures are known and acceptable, however, we will test both existing and new measures for their applicability to this study population. Drafts of all items are provided in the baseline survey (**Appendix H**).

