13.2. Sample size/ power analyses

Power calculations were estimated using Mplus by creating a Monte Carlo Simulation by generating a synthetic data set based on the expected parameter values, such as slopes, standard errors, and correlations among measured variables, for the anticipated treatment effect.^{113,114} Power was estimated assuming an intracluster correlation of 0.5, which is similar to our previous NIDA-funded studies.^{105,112,115} Statistical tests were two-sided, allowing detection of effects in either direction, and an alpha of .05 and power at 80%, corresponding to moderate effect sizes. Because the outcome is a count (i.e., Poisson), standard errors were estimated as non-normal via a sandwich estimator in Mplus.¹¹⁶ Co-Is [name] and [name] found that the number of participants who initiated people into injection was halved at follow-up.⁷ Preliminary data from MPIs [name] and [name]'s study in LA and SF indicated that 809 active PWID were found to have initiated 431 people in the past year. Using the same proportion, we expect that 573 people would be initiated by our proposed sample size of 1,076 participants at baseline (286 in each arm). If the number of people initiated by intervention group participants is halved, as suggested by [name] and [name]'s pilot data, that would represent a reduction of 143 people not being initiated into injection.

We also calculated the effect under different assumptions of attrition, subgroups (e.g., 25% Latino), sex, and age. For brevity, we illustrate power for primary outcome and most conservative—changes in the number of injection initiation events. We also account for 25% attrition—our worst-case scenario. To test the three hypotheses given our alpha and power specifications, we would need a baseline recruitment of 1,076 (n=538 per condition). We will recruit 1,076 participants to achieve the final sample of approximately 800 at the 12-month data point. The sample power for Cohen's effect sizes for small (2 percentage point difference), medium (5% difference) and large (10%–15% difference) effect sizes are plotted in **Figure 4**, revealing that after

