accounting for attrition, a final study of 800 participants at the 12month follow-up, evenly randomized, will have excellent power to detect small (0.82), moderate (0.88), and large (0.99) effect sizes. We also examined power for our mediational analyses in which the injection initiation risk variables will be differentially associated with treatment assignment. Following data from Co-I [name] for the mediational models, we expect that there was a 37% change in transition from initiation to non-initiation, and a 38% reduction in the participants injecting in front of injectionnaive people. These parameter estimates were converted to a Monte-Carlo simulation in Mplus, and we will have power to detect a mediational effect of for moderate to large pathways (Tx \rightarrow Mediator \rightarrow Outcome). Note that we will not have sufficient power for small mediational effects with our proposed sample, which may be clinically insignificant anyway.

1000

1500

High

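### Aim 3: a difference score on Yes/No mediators merges people who kept the risk with people who never had it; without the baseline mediator in the model, the mediated effect on the 12-month count is attenuated, to about half at mid-range prevalence

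*Combined protocol and SAP*

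**What the plan says.** Section 3.17 defines the three social learning mediators (injecting in front of, describing injection to, and speaking positively about it to non-injectors) over the past 6 months: "Each item is a binary variable (Yes/No) where Yes denotes endorsing the injection initiation social learning risk assessed".

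The Aim 3 text in section 13.1 gives two lagged forms and chooses neither. One is static: "The lagged approach can be used as static measures at 6 months and 12 months". The other uses "changes in injection initiation social learning risks and IMB skills constructs that precede changes in the number of counts of initiation as outcome", and this second form is described as strong because "the change in a variable, created by difference scores, is isolated so that it precedes the subsequent outcome".

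On the outcome, the same section says: "The outcome variable will remain counts of the number of episodes initiating someone into drug injection", with requests to initiate as the other count, and it names the 12-month count as the outcome for the 6-month mediators. It also plans a separate model with mediator and outcome both measured at 6 months.

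No covariates are listed for the mediation models. The rules elsewhere in section 13.1 admit variables that differ by condition at baseline or are linked to loss to follow-up, with optional terms for fidelity and site.

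**The concern.** A 0-to-6-month difference on a Yes/No item takes three values: -1 (stopped), 0 (no change) and +1 (took it up). The 0 group holds two opposite kinds of participant: those who still do the thing that H3 says drives initiation, and those who never did. If later initiation depends on whether the risk is present, the score discards much of that information.

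H3 is one of the three hypotheses. Section 13.2 already concedes that the sample cannot detect small mediated effects, so avoidable attenuation could help turn a real mediator into a null finding. H1 and H2 are not affected.

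**Working it through.** **Inputs.** From the documents: binary mediators (3.17); difference score (13.1); "a 38% reduction in the participants injecting in front of injectionnaive people" (13.2), applied here as CTC prevalence = 0.62 x control prevalence at 6 months, which is an assumption about its use. The documents give no baseline prevalence, no correlation between visits, no mediator-outcome effect and no numerical power for mediation, so there is no stated figure to reproduce. Those quantities are assumed below.

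**Step 1: coding.** Let M0 and M6 be the item at baseline and 6 months, and D = M6 - M0. Yes/Yes gives 1 - 1 = 0; No/No gives 0 - 0 = 0.

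**Step 2: CTC-to-mediator path.** Randomisation balances M0, so the arm difference in D equals that in M6. A simulation at baseline prevalence 0.5 gave -0.190 and -0.189. Any loss therefore falls on the mediator-outcome path, and the mediated effect shrinks by the same factor.

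**Step 3: mediator-outcome path, 12-month count as outcome, M0 not in the model.** Suppose the mean count depends on M6 with slope b. Within arm, with variances V0 and V6 and covariance C,

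slope on D = b x (V6 - C) / (V0 + V6 - 2C).

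If V0 = V6 = V, this is b(V - C)/(2V - 2C) = b/2, whatever the correlation.

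**Step 4: range.** Factor on b, control prevalence unchanged, CTC at 0.62, correlations from 0 up to 0.6 where feasible:

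| Baseline prevalence | Factor |
|---|---|
| 0.2 to 0.6 | 0.39 to 0.50 |
| 0.7 to 0.8 | 0.52 to 0.60 |
| 0.9 | 0.65 to 0.71 |
| 0.95 | 0.75 to 0.80 |

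Example, prevalence 0.7, correlation 0: V0 = 0.7 x 0.3 = 0.210. V6 is 0.210 in controls and 0.434 x 0.566 = 0.246 in CTC, mean 0.228. Factor = 0.228/(0.210 + 0.228) = 0.52. If controls also fall by 20%, the range widens to 0.29 to 0.88.

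**Step 5: a worked case.** Assume 70% have the risk at baseline; in controls 80% of these keep it and 30% of the others take it up; CTC multiplies both by 0.62; mean 12-month count is 0.10 without and 0.40 with the 6-month risk.
- 6-month prevalence: control 0.7 x 0.80 + 0.3 x 0.30 = 0.650; CTC 0.62 x 0.650 = 0.403. Arm difference -0.247.
- True mediated effect: -0.247 x 0.30 = -0.074.
- Scoring 0: control 0.56 + 0.21 = 0.770; CTC 0.347 + 0.244 = 0.591; average 68%, two thirds of them Yes at both visits.
- Averaged over arms: V6 = (0.2275 + 0.2406)/2 = 0.2341; C = 0.21 x (0.50 + 0.31)/2 = 0.0851.
- Factor = (0.2341 - 0.0851)/(0.2100 + 0.2341 - 0.1701) = 0.1490/0.2740 = 0.54. Mediated effect with D: -0.040.

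At 50% and 85% baseline prevalence the factor is 0.48 and 0.69.

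**Step 6: counts on the log scale.** A simulation of 300,000 records (half structural zeros, mediator rate ratio 3, log 1.10; prevalence 0.3 to 0.9) gave mediated effects of 0.45 to 0.64 of full size with D alone.

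**Step 7: adding M0.** Because M6 = D + M0, a model with arm, D and M0 gives the same mediator coefficient as one with arm, M6 and M0. In the simulation the log rate ratio returned to 1.08 to 1.13.

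**Step 8: change in counts, 6 to 12 months, as outcome.**
- 12-month count follows M6 and 6-month count follows M0, same slope b: the change is bM6 - bM0 = bD. Full size (simulated 0.99 to 1.02).
- Both counts follow M6, with slopes b12 and b6: the change depends on (b12 - b6)M6. This is zero if the slopes are equal (simulated -0.02 to 0.02) and negative if the same-visit link b6 is the stronger.

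**The case against.** The strongest reply is that the change form in section 13.1 pairs the difference score with a change in counts, not with the 12-month count, and that in this pairing the path can be recovered in full. That stands as far as it goes, and it is why a reader who inferred that the plan simply halves the H3 effect would be going beyond the documents. But full recovery needs the 6-month count to follow baseline risk. Sections 3.16 and 3.17 ask about initiation and about the risks over the same past 6 months, and section 13.1 itself plans a concurrent 6-month mediation model. The section also says that the outcome remains the count and names 12 months, so the level version is a fair reading.

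Second, the baseline mediator might be in the model. Nothing excludes it, but the stated covariate rules would normally leave it out, because randomisation should balance it.

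Third, equal variance is doubtful, because section 2.0 enrols "people who inject drugs (PWID) who report having initiated someone or having injection initiation social learning risks in the past 6 months (N=1,076"). High prevalence weakens the attenuation, as Step 4 shows, though it does not remove it. Entry is by any of several routes, so no single item need be near 100%.

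Fourth, change scores have a recognised purpose, which is to remove stable differences between people. Adjusting for M0 does not remove an unmeasured trait that drives both risk and initiation. In two assumed examples the adjusted log rate ratio was 1.43 and 1.79 against a true 1.10, that is 1.3 and 1.6 times too large. The adjusted model is better specified but should not be presented as unbiased.

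Two further inferences are not supported. The plan does not make the change form its preferred model; it is one option, favourably described. Nor is a large loss of power established. With means of 0.15 v 0.25 and 800 participants, simulated power was 47% with the difference score against 81% with M6 adjusted for M0 (5% v 65% if baseline risk also adds 0.10 to the mean). With the 0.10 v 0.40 of Step 5, whose mediator effect is three times as large, it was 100% v 100% (90% v 100%).

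**Conclusion.** The point holds conditionally and should be acted on. The coding fault follows directly from sections 3.17 and 13.1. For the 12-month count without the baseline mediator, the attenuation is to about half when the risk has similar variance at the two visits, and to roughly 0.4 to 0.8 over assumed prevalences of 20% to 95% with controls unchanged. These factors assume that the count depends on 6-month risk only. If baseline risk also marks stable risk, adding 0.10 to the mean, the factor in the Step 5 case falls from 0.54 to 0.39. For the change in counts, the answer runs from full size to zero or reversed, depending on a timing assumption that the plan does not state.

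The point concerns the three binary items in one of several Aim 3 analyses. It does not extend to the static option or to IMB constructs scored as scales.

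**What to change.** In the Aim 3 text of section 13.1, for the binary social learning items:

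- Specify the lagged H3 model as the 6-month item as mediator and the 12-month count as outcome, with the baseline mediator as a covariate in both the mediator and the outcome equations.
- If a difference-score version is kept, include the baseline mediator in it too and label it a sensitivity analysis.
- Remove or qualify the description of the change form as strong.
- State that confounding of the mediator-outcome path by unmeasured stable traits remains possible.

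The cost is a few sentences and one covariate per mediator, already collected at baseline. No change to data collection or sample size is needed.
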